Clinical Study Protocol

I. Protocol Title:

[figure not shown]
A Single-center, Retrospective Study to Evaluate the Clinical Performance of Artificial Intelligence Medical Assisted Diagnostic Software (VeriSee DR) for Screening of Diabetic Retinopathy (DR) in Patients with Diabetes Mellitus.

II. Objectives:

This study is to evaluate the clinical performance of VeriSee DR for Diabetic Retinopathy from color fundus photography images. The sensitivity and specificity of VeriSee DR's automated image analysis for screening the DR will be determined.

III. Investigational products:

1. Name: VeriSee DR
2. Method of analysis: VeriSee DR is a software as medical device that incorporates an artificial intelligence (AI)-based algorithm to evaluate the Diabetic Retinopathy (DR) from color fundus photography images screening. The screening result of DR will be determined as referable DR or non-referable DR by VeriSee DR.
3. Method of analysis: VeriSee DR is a software as medical device that incorporates an artificial intelligence (AI)-based algorithm to evaluate the diabetic retinopathy (DR) from color fundus photography images screening. The screening result of DR will be determined as referable DR or non-referable DR by VeriSee DR.

4. Intended use: VeriSee DR is intended to screen DR from the images taken by color fundus photography, which can assist the physicians to assess whether further examination for retinopathy by the ophthalmologist is needed. VeriSee DR only provides the screening results of DR for the physicians' reference and VeriSee DR is not intended to diagnose of DR or treat DR.
5. Device type: Software as a medical device (SaMD)

IV. Endpoint:

1. Primary endpoint:
 - To evaluate the clinical performance of VeriSee DR by determining the sensitivity and specificity.
2. Secondary endpoints:

Clinical Study Protocol

- To evaluate the clinical performance of VeriSee DR by determining the positive and negative predictive values (PPV and NPV)

V. Selection criteria:

The screening by inclusion and exclusion criteria for eligibility of subjects will be performed by the information technology office at the clinical site. A dedicated ophthalmologist will be responsible to confirm the eligibility of enrolled subjects' color fundus photography images for inclusion criterion # 4 and exclusion criterion # 2.

1. Main inclusion criteria:

- Subject with age \geq 20 years old
- Subject with documented diagnosis of diabetes mellitus
- Subject with image taken by color fundus photography that meet the following requirement:
 - The resolution of image is 1024×1024 pixels or higher;
 - The angle view of image is 45 or 50 degree.
- Subject's image includes macula and optic nerve as judged by the ophthalmologist.

2. Main exclusion criteria:

- The color fundus photography image previously used by VeriSee DR during the development process and pre-clinical test
- The macula, optic nerve, or other part in the image of color fundus photography is unclear to determine the disease condition as judged by the ophthalmologist.

VI. **Study procedures:** This is a single-center, retrospective study to evaluate the performance of VeriSee DR for screening of potential diabetic retinopathy (DR). The sensitivity and specificity of VeriSee DR will be determined in this study by comparing the results of gold standard, which is the judgment of DR by the ophthalmologists (evaluators).

Clinical Study Protocol

International Clinical Diabetic Retinopathy Disease Severity Scale		
Stage	Proposed Disease Severity Level	Findings Observable upon Dilated Ophthalmoscopy
0	No apparent retinopathy	No abnormalities
1	Mild non-proliferative diabetic retinopathy (NPDR)	Microaneurysms only
2	Moderate NPDR	More than just microaneurysms but less severe NPDR
3	Severe NPDR	Any of the following and no signs of PDR 
 • More than 20 intraretinal hemorrhages in each of 4 quadrants • Definite venous beading in 2 or more quadrants • Prominent IRMA in 1 or more quadrants
4	Proliferative diabetic retinopathy (PDR)	One of both of the following: 
 • Neovascularization • Vitreous/preretinal hemorrhage

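### Must the protocol tie the secondary endpoints PPV and NPV to a stated prevalence or screening population?

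*Protocol*

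**What the plan says.** Section IV.1 sets the primary endpoint: "To evaluate the clinical performance of VeriSee DR by determining the sensitivity and specificity". Section IV.2 adds the only secondary one: "To evaluate the clinical performance of VeriSee DR by determining the positive and negative predictive values (PPV and NPV"). Neither gives a prevalence, a target value or an interval method.

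Section III describes a two-way device output: "The screening result of DR will be determined as referable DR or non-referable DR by VeriSee DR". Under intended use, section III.4 says of the images or the software result, "which can assist the physicians to assess whether further examination for retinopathy by the ophthalmologist is needed".

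Section VI describes the design: "This is a single-center, retrospective study to evaluate the performance of VeriSee DR for screening of potential diabetic retinopathy (DR"). Section V says that eligibility screening "will be performed by the information technology office at the clinical site". The listed criteria cover a minimum age of 20, diabetes ("Subject with documented diagnosis of diabetes mellitus"), image resolution and angle, macula and optic nerve in view, earlier use of the image in development, and clarity. On clarity, an image is excluded when a relevant part "is unclear to determine the disease condition as judged by the ophthalmologist". No listed criterion mentions retinopathy diagnosed or treated before the image was taken. The text does not say how images are drawn from the archive. Both lists are headed as the main criteria.

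**The concern.** PPV and NPV are what a physician acting on a single result wants to know: the chance that a flagged patient has referable DR, and the chance that a cleared patient does not. Unlike sensitivity and specificity, both depend directly on how common referable DR is among the subjects tested.

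The device is meant for screening, yet the images come from one site's archive. Their referable-DR fraction could be that of routine screening, or that of a clinic following patients with known retinopathy. With no prevalence named in IV.2 and no rule on prior DR in section V, a reader could take the observed predictive values as those to expect in screening. If the fractions differ, PPV could be off by a wide margin in either direction.

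**Working it through.** **Inputs.** The Protocol states no sensitivity (Se), specificity (Sp), referable-DR fraction (p) or sample size, so it has no figure to reproduce. The values below are assumptions.

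**Formulas.**

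- PPV = Se·p / [Se·p + (1 − Sp)(1 − p)]
- NPV = Sp(1 − p) / [Sp(1 − p) + (1 − Se)p]

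**Step 1: how far the values move.** With Se = Sp = 0.90:

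| p | PPV | NPV |
|---|---|---|
| 5% | 0.045/(0.045 + 0.095) = 0.321 | 0.855/(0.855 + 0.005) = 0.994 |
| 10% | 0.09/(0.09 + 0.09) = 0.500 | 0.81/(0.81 + 0.01) = 0.988 |
| 20% | 0.18/(0.18 + 0.08) = 0.692 | 0.72/(0.72 + 0.02) = 0.973 |
| 30% | 0.27/(0.27 + 0.07) = 0.794 | 0.63/(0.63 + 0.03) = 0.955 |
| 40% | 0.36/(0.36 + 0.06) = 0.857 | 0.54/(0.54 + 0.04) = 0.931 |

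Over Se = Sp from 0.80 to 0.95, PPV runs from 0.308 to 0.679 at 10% and from 0.727 to 0.927 at 40%. The dependence on p is real.

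**Step 2: the direction.** Take 20% as the screening prevalence and Se = Sp = 0.90. A 40% sample overstates PPV by 0.857 − 0.692 = 0.165 and understates NPV by 0.973 − 0.931 = 0.042. A 10% sample understates PPV by 0.692 − 0.500 = 0.192 and overstates NPV by 0.988 − 0.973 = 0.015. Nothing in the Protocol says which case applies, or whether either does.

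**Step 3: does the plan lose the information?** Suppose 1000 subjects, 400 of them with referable DR, and Se = Sp = 0.90. The two-by-two table holds 360 true positives, 40 false negatives, 60 false positives and 540 true negatives.

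- Secondary endpoints: PPV = 360/420 = 0.857 and NPV = 540/580 = 0.931.
- Primary endpoint: Se = 360/400 = 0.90 and Sp = 540/600 = 0.90.
- Sample fraction: 400/1000 = 40%.

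Putting this Se and Sp into the formulas at p = 20% gives 0.692 and 0.973, the values in the table above. The counts that the endpoints already require therefore yield the sample fraction and the predictive values at any chosen prevalence. No extra data are needed.

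**Step 4: is any passage wrong or contradicted?** IV.2 says that PPV and NPV will be determined. It does not say that they apply outside the sample. III.4 describes a referral aid and does not limit it to patients without known DR, so including such patients breaks no stated rule. Followed as written, the plan gives correct sample values for all four measures.

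**The case for a change.** The strongest reply is that recalculation does not cure everything. If patients with known, more advanced DR are over-represented, whole-sample sensitivity may itself be too high for screening. Suppose half of the positives had known DR with Se 0.97 and half did not with Se 0.80. Whole-sample Se is then 0.5 × 0.97 + 0.5 × 0.80 = 0.885. At 10% prevalence, 1000 screened subjects include 100 cases. Of these, 100 × (1 − 0.885) = 11.5 would be expected to be missed, against 100 × (1 − 0.80) = 20.0 using the second group's own sensitivity. Who is eligible and how images are sampled are also protocol matters, not ones for a statistical analysis plan.

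The logic is sound, and it would matter if the documents pointed to such a sample. They do not. The 0.97, the 0.80 and the even split are all assumed. The Protocol describes no enrichment, and silence in two lists headed as main criteria is weak evidence. The point also concerns the severity mix behind sensitivity more than the choice of PPV and NPV in IV.2. An analysis restricted to subjects without prior DR would need a dated records query, whose feasibility the Protocol does not establish, and it would widen the intervals. At an observed sensitivity of 0.90, the 95% Wilson interval is 0.826 to 0.945 with 100 positives and 0.786 to 0.957 with 50.

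The exclusion of unclear images could also shift the referable-DR fraction, but in an unknown direction, and this gives no ground for a change.

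**Conclusion.** No change to the plan is needed. It is true that IV.2 names no prevalence, and that the observed PPV and NPV will hold only at the sample's own referable-DR fraction. That is a property of predictive values in any diagnostic study, and IV.2 claims nothing beyond it. The possible gap is sizeable for PPV (0.165 to 0.192 in the two examples against 20%) and small for NPV (0.015 to 0.042), but these figures rest on assumed accuracy and prevalence, and the direction is unknown.

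The primary endpoint is untouched by prevalence and supplies what is needed to recalculate. An analyst would sensibly print the referable-DR fraction beside PPV and NPV, and could add values with 95% intervals over a prevalence range chosen before analysis. This is optional reporting detail of a kind usually left to a statistical analysis plan, which may exist but is not at hand. The conclusion would change if the documents showed deliberate enrichment with referable cases, or presented the sample PPV and NPV as screening values. They do neither.

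### Does admitting subjects with already recorded diabetic retinopathy, without asking for that history, make the study unfit for its screening purpose?

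*Protocol*

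**What the plan says.** The title states the purpose and the population together: "for Screening of Diabetic Retinopathy (DR) in Patients with Diabetes Mellitus". Section V.1 lists four main inclusion criteria: an age limit of 20 years, "Subject with documented diagnosis of diabetes mellitus", an image of set resolution and angle, and "Subject's image includes macula and optic nerve as judged by the ophthalmologist". Section V.2 lists two main exclusions. One is "The color fundus photography image previously used by VeriSee DR during the development process and pre-clinical test"; the other is an image too unclear to judge. None of the six concerns an earlier DR diagnosis or DR treatment.

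The intended use (III.4) is that the software can "assist the physicians to assess whether further examination for retinopathy by the ophthalmologist is needed". Section VI gives the study's purpose as to "evaluate the performance of VeriSee DR for screening of potential diabetic retinopathy (DR"). The endpoints (IV) are sensitivity and specificity (primary) and PPV and NPV (secondary), with no split by history. On who selects the subjects, section V says: "The screening by inclusion and exclusion criteria for eligibility of subjects will be performed by the information technology office at the clinical site".

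**The concern.** Screening is often understood as looking for disease that nobody has yet found. On that reading, a person whose DR is already diagnosed or treated is not a screening candidate, and a retrospective search of one site's records could return many such people.

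Two things would then be at stake. First, sensitivity or specificity might differ between subjects with and without a DR record, so that the pooled value describes neither group. Second, the share with referable DR might differ, and this alone shifts PPV and NPV even if the software performs identically in both groups. If the history is never captured, a reader interested only in people without a DR record could not separate the two groups. Because section V settles who enters and who searches the records, the protocol seems the natural place to ask for it.

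**Working it through.** **Step 1. Compare the declared population with the enrolled population.**

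| Place | What it fixes about the population |
|---|---|
| I, title | Patients with diabetes mellitus |
| III.4, intended use | Colour fundus images; helps decide on referral to an ophthalmologist; no limit by DR history |
| V.1 and V.2 | Documented diabetes, age, image requirements; no limit by DR history |
| VI | Screening of potential DR; no limit by DR history |

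The four places agree. The referral decision appears only in III.4; section VI speaks of screening without defining who is to be screened. A mismatch arises only if one adds the condition that the target is people without known DR, and no sentence in the document states that condition.

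**Step 2. Is there a figure to reproduce?** No. The text shown gives no sample size, prevalence, target sensitivity or specificity, or share of subjects with a DR record. Every input below is an assumption.

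**Step 3. Predictive values.** Assume sensitivity 0.85 and specificity 0.90 in both groups, and 10% referable DR among subjects without a record. Let *w* be the share of the sample with a record and *p1* the proportion of them with referable DR. Then

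- *p* = (1 - *w*) × 0.10 + *w* × *p1*
- PPV = 0.85*p* / (0.85*p* + 0.10(1 - *p*))
- NPV = 0.90(1 - *p*) / (0.90(1 - *p*) + 0.15*p*)

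For subjects without a record (*p* = 0.10): PPV = 0.085/0.175 = 48.6% and NPV = 0.810/0.825 = 98.2%. Differences are pooled minus no-record, in percentage points.

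| *p1* | *w* | *p* | PPV | Difference | NPV | Difference |
|---|---|---|---|---|---|---|
| 0.50 | 0.1 | 0.14 | 58.0% | +9.5 | 97.4% | -0.8 |
| 0.50 | 0.4 | 0.26 | 74.9% | +26.3 | 94.5% | -3.7 |
| 0.30 | 0.1 | 0.12 | 53.7% | +5.1 | 97.8% | -0.4 |
| 0.30 | 0.4 | 0.18 | 65.1% | +16.5 | 96.5% | -1.7 |
| 0.10 | any | 0.10 | 48.6% | 0 | 98.2% | 0 |
| 0.05 | 0.1 | 0.095 | 47.2% | -1.4 | 98.3% | +0.1 |
| 0.05 | 0.4 | 0.08 | 42.5% | -6.1 | 98.6% | +0.4 |

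**Step 4. Sensitivity and specificity.** If a share *k* of positives has a record, the pooled sensitivity differs from the no-record value by *k* × (*s* - 0.85), where *s* is the sensitivity in subjects with a record. For *k* from 0.1 to 0.7 this is +1.3 to +9.1 points if *s* = 0.98, zero if *s* = 0.85, and -1.5 to -10.5 points if *s* = 0.70. Likewise, if a share *j* of negatives from 0.05 to 0.3 has a record and specificity is 0.90 in the rest, the difference is -0.5 to -3.0 points if theirs is 0.80, zero if 0.90, and +0.25 to +1.5 points if 0.95.

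**Step 5. Read the results.** The formulas are right, but the sign and size come entirely from the assumed inputs. Nothing in the protocol favours one row over another. The table shows that PPV and NPV depend on case mix, which is true of every accuracy study that reports them. It does not show that this study's case mix departs from the population it declares.

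**The case for a change.** The strongest case on the other side is practical. No listed criterion bars or records prior DR. PPV and NPV are declared endpoints and depend on the share with referable DR. A reader judging use before referral would like to see results in subjects without a DR record. One yes/no field and one table would supply them without changing eligibility or the primary analysis, and no analysis can use a field that nobody collected.

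The facts and the usefulness of the addition stand. The step from there to a defect does not, for three reasons.

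- A supportive subgroup table is ordinary content of a statistical analysis plan, and a history field is ordinary content of a data-extraction form. Neither document is at hand. The criteria are headed as the main ones, and the text shown ends at the severity scale, so silence here does not show that the history goes uncollected.
- The argument about a lost opportunity is weak in a retrospective study. The site searches records that already exist, and nothing shown prevents a later query of them, although that would mean a second extraction.
- The table would answer the narrower question only in part. Its PPV and NPV would still carry one centre's case mix, and having no record at the site does not mean having no known DR. Take *w* = 0.2 and *p1* = 0.50, so that pooled *p* = 0.18 and pooled PPV = 65.1%, which is 16.5 points above 48.6%. If 20% of prior records are missed, the no-record stratum has *p* = (0.8 × 0.10 + 0.2 × 0.2 × 0.50)/(0.8 + 0.04) = 0.119 and PPV = 53.5%, so 4.9 of the 16.5 points remain.

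**Conclusion.** The concern does not hold. The enrolled population is the one the protocol declares, and the protocol nowhere restricts its claim to people without known DR. On this point, pooled sensitivity, specificity, PPV and NPV estimate what the protocol sets out to estimate. The document contains no contradiction here, no wrong figure and no demonstrated bias. The illustrative PPV differences of -6.1 to +26.3 points rest wholly on assumed inputs and include zero.

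This conclusion rests on reading the target population from the title, III.4, V and VI as written. Had any of them limited the claim to people without a previous DR diagnosis, the open criteria would conflict with it. Recording the history and reporting the no-record group remains a reasonable optional addition, but the protocol is not wrong without it.

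### Exclusion criterion 1 removes the image used in development, not the patient, so another image of a patient whose image trained or tuned VeriSee DR can still enter the test set

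*Protocol*

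**What the plan says.** Protocol section V.2, first bullet, excludes "The color fundus photography image previously used by VeriSee DR during the development process and pre-clinical test". It does not mention the patient, the fellow eye or other visits.

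Three other parts of the protocol bear on which unit is meant:

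- **Section V.1, third bullet**, is worded by subject: "Subject with image taken by color fundus photography that meet the following requirement". The requirements that follow concern only resolution and a 45 or 50 degree view.
- **Section V.2, second bullet**, is worded by image: "The macula, optic nerve, or other part in the image of color fundus photography is unclear to determine the disease condition".
- **Section V, introduction**, uses both units. It says "The screening by inclusion and exclusion criteria for eligibility of subjects will be performed by the information technology office at the clinical site", and then has an ophthalmologist confirm "eligibility of enrolled subjects' color fundus photography images for inclusion criterion # 4 and exclusion criterion # 2". No second check is described for exclusion criterion 1.

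Section VI describes the design: "This is a single-center, retrospective study to evaluate the performance of VeriSee DR". The primary endpoint in section IV.1 is "To evaluate the clinical performance of VeriSee DR by determining the sensitivity and specificity". The protocol does not say where the development images came from.

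**The concern.** Images of one patient are correlated: the two eyes share disease stage and general fundus appearance, and repeat photographs of one eye resemble each other closely. Separating training from test data image by image therefore does not make them independent. An algorithm may do better on a new photograph of a patient it has learned from than on a patient it has never seen.

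At stake is the primary endpoint. If this center's archive fed training or tuning and is now also the source of the test images, sensitivity and specificity could both be overstated for the patients who matter, those new to the software. With one center, no other site dilutes the overlap. Images used only in the pre-clinical test would not be expected to cause this bias, because the algorithm did not learn from them.

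**Working it through.** **Step 1: does any listed criterion remove the other images?** Take a patient aged 20 or over with documented diabetes whose right-eye image was used in training. Offer a left-eye image of adequate resolution and field that shows the macula and optic nerve clearly.

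| Criterion | Result for the left-eye image |
|---|---|
| Inclusion 1 and 2 (age, diabetes) | met |
| Inclusion 3 (resolution, angle of view) | met |
| Inclusion 4 (macula and optic nerve in the image) | met |
| Exclusion 1 (image used before) | does not apply: this image was not used |
| Exclusion 2 (image unclear) | does not apply |

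The image is eligible on the literal text. The same holds for a same-eye repeat or an image from another visit.

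**Step 2: is the unit settled elsewhere?** No. All four inclusion criteria are worded by subject and section V speaks of subject eligibility, which permits a subject-level reading. Both exclusion criteria are worded by image, and the ophthalmologist confirms images. Two careful readers could assemble different test sets.

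**Step 3: how large could the bias be?** The protocol gives no overlap, sample size or expected performance, so there is no figure to reproduce. Define:

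- f: the overlapping fraction, among reference-positive units for sensitivity and among reference-negative units for specificity;
- g: performance on other images of development patients minus performance in unseen patients.

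Observed performance = (1 − f) × unseen + f × overlap, so bias = f × g.

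Both inputs below are assumptions, with g set at 0 to 10 percentage points:

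| f | g = 0 | g = 2 | g = 5 | g = 10 |
|---|---|---|---|---|
| 5% | 0 | 0.1 | 0.25 | 0.5 |
| 10% | 0 | 0.2 | 0.5 | 1.0 |
| 20% | 0 | 0.4 | 1.0 | 2.0 |
| 50% | 0 | 1.0 | 2.5 | 5.0 |

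(Bias in percentage points.)

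A worked case, with assumed sensitivity 0.85 in unseen and 0.95 in overlapping patients and f = 20%: 0.80 × 0.85 + 0.20 × 0.95 = 0.68 + 0.19 = 0.87, which is 2 points too high.

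The overlap needed for a bias of 1 point is 1/10 = 10% at g = 10, 1/5 = 20% at g = 5 and 1/2 = 50% at g = 2. At g = 0 or f = 0 there is none.

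**The case against.** The strongest reply is that the harm depends on a fact the protocol does not give. Bias needs this center to have supplied training or tuning images, and other images of the same patients to reach the test set. This stands, and the finding is conditional on it.

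Second, what is screened and enrolled is the subject, so a subject with a previously used image may be meant to fail criterion 1. Image wording is also natural for an image-quality rule, so criterion 2 says little about the unit in criterion 1. This stands in part. The subject-level reading is possible, but it is not stated, and a subject screened on a different image passes the literal rule.

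Third, both lists are headed as main criteria and may not be exhaustive. True, but nothing in the protocol points to a further rule at patient level.

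Fourth, g may be near zero, because the training images themselves are already excluded. As defined it also mixes leakage with case-mix differences and could even be negative. This is correct. The table shows scale under assumptions and is not an estimate; the upward direction is the expected effect of leakage alone.

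Finally, a patient-level match needs an identifier link that may not exist. This limits the remedy but does not remove the gap.

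**Conclusion.** The concern holds. As written, exclusion criterion 1 separates development and test data by image and leaves patient-level overlap open. The wording gap can be verified from the text. Its consequence is conditional: upward bias in sensitivity and specificity arises only if this center supplied training or tuning images, other images of those patients enter the test set, and the software does better on them than on unseen patients.

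The size is unknown. Under the assumed gain of 0 to 10 points it is 0 to 0.5 points at 5% overlap, 0 to 1.0 at 10% and 0 to 2.0 at 20%. It is zero if the center supplied no such images. The point should be fixed because the repair is cheap and protects the primary endpoint; it does not by itself invalidate the study. Confidence is medium. This is not a matter to leave to an analysis plan: the eligibility rule decides which images are extracted, and overlapping patients cannot be identified afterwards unless the identifier link is made.

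**What to change.** Replace exclusion criterion 1 with:

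> (a) Any subject with one or more color fundus photography images (either eye, any visit) used to train or tune VeriSee DR, matched on subject identifier; (b) any other color fundus photography image used in the development process or the pre-clinical test of VeriSee DR.

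Part (b) keeps the protection the protocol already has. In addition, state whether this center supplied development images, and report the number of subjects excluded under (a). If no identifier link to the training and tuning images exists, say so as a limitation.

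The cost is a reworded criterion, one match on subject identifier and one reported count. If the center supplied no training or tuning images, no subject is lost and the question is closed. Otherwise some eligible subjects are lost, and their removal could shift the case mix. Without the link, the overlap cannot be identified and can only be disclosed.

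### Does a gold standard worded as plain DR, set against a referable/non-referable output, make the primary sensitivity wrong?

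*Protocol*

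**What the plan says.** Section III (items 2 and 3, which carry the same text) describes the software's output: "The screening result of DR will be determined as referable DR or non-referable DR by VeriSee DR". Item 4 of that section gives the purpose, which is to help physicians "assess whether further examination for retinopathy by the ophthalmologist is needed".

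Section II states the objective: "The sensitivity and specificity of VeriSee DR's automated image analysis for screening the DR will be determined". The primary endpoint in section IV is "To evaluate the clinical performance of VeriSee DR by determining the sensitivity and specificity", and the secondary endpoint adds "determining the positive and negative predictive values (PPV and NPV" to the same comparison. Neither endpoint names the condition that counts as positive.

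Section VI defines the comparison as "comparing the results of gold standard, which is the judgment of DR by the ophthalmologists (evaluators". The table that follows is the "International Clinical Diabetic Retinopathy Disease Severity Scale", with stages 0 (no apparent retinopathy) to 4 (proliferative disease). No stage in it is marked as referable or as reference-positive.

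**The concern.** The two sides of the 2x2 table carry different labels. The software side is referable against non-referable; the evaluator side is just DR. On the printed scale stage 1 is already a named retinopathy, so a literal reader could take a judgment of DR to mean stage 1 or higher. If the software is designed to leave some of those cases unreferred, its correct calls on them would enter the primary sensitivity as misses.

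All four accuracy measures depend on which cases are reference-positive. The same images and the same software calls would then give a different table, and that table would not measure accuracy for the condition the software reports.

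**Working it through.** The protocol states no accuracy target, sample size or stage distribution, so there is no planned figure to reproduce. Two checks apply: how far the choice of reading could matter, and which reading the text supports.

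**1. How far it could matter.** All inputs are assumptions:

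- Se = 0.90, sensitivity for referable DR
- m = share of all DR that is non-referable
- f = share of that non-referable DR which the software flags

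If the evaluators' split matches the software's, sensitivity is Se = 0.90 whatever m is. Against any DR it is

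Se(any) = (1 − m) × 0.90 + m × f.

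| m | f = 0.1 | f = 0.2 | f = 0.3 |
|---|---|---|---|
| 0 | 0.90 | 0.90 | 0.90 |
| 0.2 | 0.74 | 0.76 | 0.78 |
| 0.3 | 0.66 | 0.69 | 0.72 |
| 0.5 | 0.50 | 0.55 | 0.60 |

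The difference from the matched value is m × (f − 0.90). It is negative whenever m > 0 and f < 0.90, and zero when m = 0.

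A mid case per 1000 subjects adds two assumptions: 30% have DR, and 5% of those without DR are flagged. With m = 0.3 and f = 0.2 there are 210 referable, 90 non-referable and 700 without DR, of whom 189, 18 and 35 are flagged (242 flagged, 758 not flagged).

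| | Matched split | Any DR |
|---|---|---|
| True positives / false negatives | 189 / 21 | 207 / 93 |
| False positives / true negatives | 53 / 737 | 35 / 665 |
| Sensitivity | 189/210 = 0.90 | 207/300 = 0.69 |
| Specificity | 737/790 = 0.933 | 665/700 = 0.950 |
| PPV | 189/242 = 0.781 | 207/242 = 0.855 |
| NPV | 737/758 = 0.972 | 665/758 = 0.877 |

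So the choice of reading could matter a great deal, or not at all. The protocol does not supply m, and m = 0 is open because it never says that any stage of DR falls below the software's threshold.

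**2. Which reading the text supports.**

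- Section III, item 2, calls the referable/non-referable split the screening result of DR. Plain DR is therefore the document's own short name for that split, and sections II and VI can be read as using the same shorthand.
- Section III, item 4, poses a referral question and says that the software is not meant to diagnose. That fits a referable target better than presence of any retinopathy.
- A five-level severity scale follows the gold-standard sentence. A graded scale points to a staged judgment, which can be split to match the output; a yes/no on any DR would not need five levels.
- The label non-referable DR does not show that some DR is meant to go unreferred. The output has only two values, so an eye at stage 0 must receive the same label. It can simply mean not referable.
- No sentence states that stage 1 or higher, or any DR, is reference-positive.

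**The case for a change.** The strongest case for a change is that the protocol does more than stay silent: it fixes a reference standard in words that differ from the index output, and the reference-positive condition defines the primary endpoint. Even on the matched reading a reader cannot reproduce reference-positive status, because no stage is named, and an open threshold could be settled after results are seen. If the evaluators recorded only DR yes or no, no later analysis text could recover the referable split.

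Part of this stands. The word referable appears only in the description of the software, and the available text does not say what the evaluators record. But different labels are not a contradiction when the document uses one as the name of the other. A yes/no reading form is a possibility that nothing in the text asserts, and the printed scale points away from it. The rule that turns grades into a 2x2 table is commonly held in the SAP, which was not available here. Proposed wording would also have to leave the threshold to the sponsor, and would presume that the software's output is defined on the printed scale, which the protocol does not say.

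**Conclusion.** No change to the plan follows. The protocol leaves the reference-positive condition unnamed, but its more natural reading compares like with like, and on that reading sensitivity is not distorted. The fall from 0.90 to between 0.50 and 0.78 rests on the less likely reading and on assumed values of sensitivity, m and f. Those values leave out m = 0, where nothing is lost. The amount cannot be calculated from the protocol.

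This judgment rests on the evaluators' grades being split by the same definition of referable as the software's output. It would need to be revisited if the SAP or the reading form made any DR the positive condition.
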